## 1.0 PROTOCOL SUMMARY AND/OR SCHEMA

### **Title: A Phase Ib/Ila Study of Romidepsin in Combination with Lenalidomide in Adults with Relapsed or Refractory Lymphomas and Myeloma**

#### **Objectives**

The primary objective of this study is:

To define the maximum tolerated dose and characterize the safety and toxicity of the combination of lenalidomide and romidepsin.

The secondary objectives of this study are to evaluate:

1. Overall response rate and clinical benefit rate (in myeloma patients)
2. Complete response rate
3. Very good partial response/partial response rate
4. Time to response
5. Duration of response
6. Event free survival

**Patient Population:** Relapsed or refractory lymphomas and multiple myeloma

**Number of Patients:** 67

**Study Design and Methodology:** This will be a multicentered, open label, phase Ib/Ila trial of romidepsin and lenalidomide in patients with relapsed or refractory lymphomas or multiple myeloma.

**Treatments Administered:** Romidepsin will be administered intravenously on days 1, 8, and 15 of a 28-day cycle. Lenalidomide will be taken orally daily for 21 days of a 28-day cycle. Maximum tolerated dose (MTD) to be determined in the phase Ib portion.

**Safety Data Collected:** The following evaluations will be conducted to assess the safety of the combination of romidepsin and lenalidomide:

- Phase Ib: Determine the MTD by NCI-CTCAE v4.0.
- Phase Ila: Further assess the combination's toxicity profile by NCI-CTCAE v4.0.

**Efficacy Data Collected:** Disease specific evaluations will be conducted to assess the efficacy of the combination of romidepsin and lenalidomide:

- Phase Ila portion (including phase Ib treated at MTD) - overall response rate, and clinical benefit rate (in myeloma patients), time to response, duration of response, and event-free survival.

## 2.0 OBJECTIVES AND SCIENTIFIC AIMS

### **The primary objectives of this study are:**

- To define the maximum tolerated dose and characterize the safety and toxicity of the combination of lenalidomide and romidepsin.

### **The secondary objectives of this study are:**

- To assess the overall response rate (ORR) and the clinical benefit rate (CBr) of lenalidomide and romidepsin.
- To assess the time to response (TTR), duration of response (DOR), and event free survival (EFS).

## 3.0 BACKGROUND AND RATIONALE

### 3.1 Romidepsin

#### 3.1.1 Romidepsin: Mechanisms of action

Romidepsin is a unique bicyclic depsipeptide originally isolated from *Chromobacterium violaceum* strain 968. [Ueda H, 1994] Results of early nonclinical studies showed that romidepsin inhibited the growth of the Ha-ras-transformed NIH3T3 clonal cell line, Ras-1, and induced reversion of the transformed morphology to normal within 1 day at a concentration of 2.5 ng/mL. [Ueda H, 1994] While mRNA expression of the c-myc oncogene in Ras-1 cells was decreased in the presence of romidepsin, Ha-ras mRNA expression was unaffected by 24-hour exposure to 2.5 ng/mL of romidepsin. Furthermore, romidepsin blocked cell cycle transition from G0/G1 to S phase and induced nuclear quiescence. The course of c-myc suppression paralleled that of G0/G1 arrest and correlated with the morphologic reversion of the transformed cells. These results led to the proposal that the growth inhibition and G0/G1 arrest resulted from romidepsin blocking the ras-mediated signal transduction pathway. [Fecteau K, 2002] Other investigations of the effect of romidepsin on G1 to S transition of the cell cycle showed that romidepsin inhibits signal transduction through MAP kinase and causes p53- independent G1 arrest. [Sandor V, 1998; Sandor V, 2000] Romidepsin has also been identified as a potent histone deacetylase (HDAC) inhibitor similar to trichostatin A based on its ability to cause arrest of the cell cycle at both G1 and G2/M phases, to induce internucleosomal breakdown of chromatin, and to inhibit intracellular HDAC activity resulting in an accumulation of marked amounts of acetylated histone species within M-8 cells. [Nakajima Y, 1998]

#### 3.1.2 Romidepsin: Pre-clinical Antitumor Activity

Potent antitumor effects of romidepsin have been demonstrated both *in vitro* and *in vivo*. [Ueda H, 1998; Ueda H, 1998] *In vitro*, romidepsin exerted antiproliferative activity against 12 human solid tumor cell lines (IC50 ranged from 0.5 to 5.9 nM), but was less potent against cultured normal cells. Moreover, a prolonged exposure

to romidepsin subsequently lowered the concentration of drug necessary to induce the antiproliferative activity. Similar IC50 values were found in a study of 13 lymphoid cell lines. [Murata M, 2000] More specifically, romidepsin was demonstrated to induce significant apoptosis in both a cutaneous T-cell lymphoma (CTCL) cell line, HUT78 and a multiple myeloma cell line. [Piekacz R, 2004]. In severe combined immunodeficiency disease (SCID) mice inoculated intraperitoneally (IP) with U-937, a histiocytic lymphoma cell line, and treated with romidepsin (0.1 to 1 mg/kg, IP) once or twice a week survived longer [median survival times of 30.5 days (0.56 mg/kg) and 33 days (0.32 mg/kg)], than saline-treated mice (20 days). Two of 12 mice treated with 0.56 mg/kg romidepsin survived past the observation period of 60 days. [Sasakawa Y, 2002]

### **3.1.3 HDAC inhibitors: Clinical Activity in Lymphoid Malignancies**

#### **3.1.3.1 Cutaneous T-cell Lymphoma (CTCL)**

The clinical activity of romidepsin was first demonstrated in a National Cancer Institute (NCI) phase I study. [Sandor V, 2002] Three patients with CTCL and 1 with significant cutaneous involvement of peripheral T-cell lymphoma (PTCL) all demonstrated a response to romidepsin at varying dose levels (12.7 to 17.8 mg/m^2). The patient with PTCL experienced a complete remission after 8 cycles of romidepsin. Subsequently, romidepsin was further evaluated in 135 evaluable subjects with CTCL in Study GPI-04-0001 and NCI Study 1312. [Rasheed W, 2008] Across all 135 evaluable subjects with CTCL, the overall response rate (ORR) was 41% (55/135) and the complete response (CR) rate was 7% (10/135). Subjects with advanced disease had a similar ORR as subjects with earlier stage disease: 42% for  $\geq$ Stage IIB and 38% for Stage I or IIA disease. Romidepsin was active in all sites of disease, including skin, lymph nodes, viscera, and blood. The median duration of response was 454 days (14.9 months). Although the median time to response was 57 days (1.9 months), in some cases an objective response to romidepsin was achieved after  $\geq$ 6 months. Across all 135 subjects included in the pooled evaluable subjects analysis set, median time to disease progression was 252 days (8.3 months). In Study GPI-04-0001, treatment alleviated pruritus in most subjects (48 of 52, 92%) who entered the study with this symptom. These data led to FDA approval of romidepsin for CTCL in September, 2009.

#### **3.1.3.2 Peripheral T-cell lymphoma (PTCL)**

In the initial Phase 2 NCI-sponsored study in 48 subjects with PTCL or other T-cell lymphomas were enrolled in addition to the CTCL patients listed above. [Piekacz R, 2005] Among all 48 subjects, the ORR (CR+PR) was 31% (15/48). The CR and PR rates were 8% (4/48) and 23% (11/48), respectively. When response was evaluated among the 34 subjects who received  $\geq$ 2 cycles of therapy, the ORR was 44% (15/34) and the CR and PR rates were 12% (4/34) and 32% (7/34), respectively.

This activity of romidepsin in PTCL was confirmed in the multi-center Phase 2 study, where 131 patients with relapsed PTCL. [Coiffier B, 2011] The objective response rate was 25% (33/130), including 15% (19/130) with CR/CRu. Response rates were not impacted by patient characteristics, prior stem-cell transplant,

number or type of prior therapies, or response to last prior therapy. The median duration of response was 17 months, with the longest response ongoing at 34+ months. Of the 19 patients who achieved CR/CRu, 17 (89%) had not progressed at a median follow-up of 13.4 months. The most common grade  $\geq 3$  adverse events were thrombocytopenia (24%), neutropenia (20%), and infections (all types, 19%). This data led to FDA approval of romidepsin for PTCL in June of 2011.

### **3.1.3.3 Multiple Myeloma (MM)**

Recently, a phase II study of Romidepsin given at 13 mg/m^2 was performed in patients with heavily pre-treated refractory multiple myeloma. [Niesvizky, 2011] Of the 12 patients enrolled no objective responses were seen and the study was unable to meet the 30% objective response criteria. Interestingly, 4 of the 12 patient with secretory myeloma had stabilization of their paraprotein and several other patients had reduction in bone pain and/or resolution of hypercalcemia. Therefore, as a single agent romidepsin showed symptomatic activity, but overall is unlikely to be efficacious in MM.

### **3.1.3.4 B-cell lymphoma**

Romidepsin has yet to be clinically studied as a single agent or in combination with other agents in B-cell lymphomas. However, other HDAC inhibitors (vorinostat, belinostat, and panobinostat) have demonstrated clinical activity in early phase studies. For example, in a combined analysis of two consecutive phase I trials in hematologic malignancies performed at MSKCC utilizing the HDAC inhibitor vorinostat of those enrolled 32 had a B-cell non-Hodgkin lymphoma (NHL). Three patients responded with one achieving a CR. [O'Connor O, 2006] Furthermore, the HDAC inhibitor panobinostat was employed in a phase II single agent study with 13 patients having relapse or refractory Hodgkin lymphoma. In this subgroup 5 or 13 achieved a partial response. [Ottman O, 2008] In a more recent study the same drug was employed specifically for relapsed disease after autologous stem cell transplantation with a ORR of 13%. [Younes, 2009] The proposed mechanism of action in B-cell lymphomas is through the proto-oncogene BCL6 that is highly active as a transcriptional repressor within the germinal B cell. Uncurbed activity of BCL6 leads to suppression of genes involved in lymphocyte activation, differentiation, cell cycle arrest, and apoptosis. Moreover, accumulation of acetylated BCL6 is known to down regulate the transcriptional repressive function allowing gene transcription of beneficial pro-apoptotic cellular products in the otherwise malignant cell. [Boreschenko O, 2002]

## **3.2 Lenalidomide**

### **3.2.1 Lenalidomide: Mechanism of action**

Lenalidomide is a proprietary IMiD® compound of Celgene Corporation. IMiD® compounds have both immunomodulatory and anti-angiogenic properties which confer antitumor and antimetastatic effects. Lenalidomide has been demonstrated to possess anti-angiogenic activity through inhibition of bFGF, VEGF, and TNF-alpha induced endothelial cell migration, due at least in part to inhibition of Akt phosphorylation response to bFGF. [Dredge K, 2005] In addition, lenalidomide has a variety of immunomodulatory effects. Lenalidomide stimulates T cell

proliferation, and the production of IL-2, IL-10 and IFN-gamma, inhibits IL-1 beta and IL-6 and modulates IL-12 production. [Corral L, 1999] Upregulation of T cell derived IL-2 production is achieved at least in part through increased AP-1 activity. [Schafer P, 2003]

### **3.2.2 Lenalidomide: Pre-clinical Antitumor Activity**

Although the exact antitumor mechanism of action of lenalidomide is unknown, a number of mechanisms are postulated to be responsible for lenalidomide's activity against lymphoid malignancies. Lenalidomide has been shown to increase T-cell proliferation, which leads to an increase in IL-2 and IFN-gamma secretion. The increased level of these circulating cytokines augment natural killer cell number and function, and enhance natural killer cell activity to yield an increase in cell lysis. [Davies F, 2001] In addition, lenalidomide has direct activity against multiple myeloma by inducing apoptosis and/or G1 growth arrest. [Hideshima T, 2000]

### **3.2.3 Lenalidomide: Clinical Activity in Lymphoid Malignancies**

#### **3.2.3.1 Multiple Myeloma**

Lenalidomide has been extensively studied in multiple myeloma as a single agent and in combination with steroids. This activity led to the randomized phase III trial of lenalidomide and dexamethasone versus dexamethasone alone. [Dimopoulos M, 2007] This study demonstrated a significant delay in time to progression as well as a survival advantage of the lenalidomide containing arm. Of note, the grade 3 and 4 neutropenia and deep venous thrombosis rates were more common in the lenalidomide containing arm. These results led to the approval of lenalidomide in combination with dexamethasone in previously treated multiple myeloma patients.

#### **3.2.3.2 Peripheral T-cell lymphoma**

Lenalidomide has been further studied in PTCL as a single agent. A multicenter phase II study in relapsed PTCL lenalidomide when dosed at 25 mg orally for 21 days of a 28-day cycle achieved a ORR of 30% with all responses being partial responses. [Deuke G, 2010] Grade 4 thrombocytopenia was seen in 33% of patients while grade 3 neutropenia was seen in 21%. Interestingly, development of a skin rash was correlated with those who obtained a response. A smaller study of lenalidomide in PTCL, also showed a 30% ORR at the same dose and schedule. [Zinzana P, 2011]

#### **3.2.3.2 Cutaneous T-cell lymphoma (CTCL)**

A small phase 2 study of lenalidomide in CTCL yielded a similar degree of activity. Among the 24 patients reported by Querfeld et al., the ORR was 32%. However in these patients dose limiting skin toxicity was seen at the 25 mg dose and a dose de-escalation to 10 mg was performed. [Querfeld, 2011] In this study significant skin tumor flare may have confounded disease assessment among the CTCL patients resulting in premature withdrawal from study due to spurious progression.

#### **3.2.3.3 B-cell lymphoma**

Lenalidomide has been further investigated in both relapsed and refractory indolent and aggressive non-Hodgkins lymphoma as well as Hodgkin lymphoma. In aggressive B-cell lymphoma 49 patients were treated with the standard 25 mg

dose taken orally for 21 days with 1 week rest. [Wiernik P, 2008] An ORR of 35% was seen with a complete response rate of 13%. Interestingly, a quarter of those who achieved a partial response at the time of first response assessment achieved further response with subsequent cycles. The toxicities were similar with a grade 4 neutropenia and thrombocytopenia of 8.2%. In indolent B-cell lymphoma lenalidomide has been studied in a similar dosing and duration strategy. The outcomes in 43 patients yielded an ORR of 23% with 7% achieving a complete response. Importantly, at the time of publication the median duration of response had not been met, but was longer than 16.5 months. Toxicities were again predictable to include grade 4 neutropenia and thrombocytopenia of 16% and 5% respectively. [Witzig T, 2009] Lastly, lenalidomide has been studied in refractory and heavily pretreated cohort of 12 patients with Hodgkin lymphoma. [Boll B, 2009] While the main objective of the study was to characterize the toxicity in this cohort 50% of the patient did achieve an objective response. Interestingly, no grade 3 or 4 toxicities were reported in this study.

### **3.3 Rationale For Combination Therapy**

Relapsed and refractory lymphoid malignancies remain an ongoing challenge with repeated courses of cytotoxic chemotherapy often yielding diminishing returns. In relapsed and refractory multiple myeloma, peripheral T cell lymphoma, and aggressive non-Hodgkin lymphoma the 5-year overall survival (OS) in transplant ineligible patients was 16%, 20%, and 32% respectively. [Kumar S, 2004; Vose J, 2008; Philip T, 1995] There remains significant need for more active therapies and combinations with many newer approaches now looking to long term or maintenance treatment employing drugs without cumulative toxicity.

In preclinical studies of Namalwa cells (derived from a Burkitt lymphoma), lenalidomide had synergistic effects with valproic acid (a known histone deacetylase inhibitor) by increasing apoptosis without adverse and potentially even beneficial effects on CD34+ progenitor cells. [Verhelle D, 2007] Furthermore, in multiple myeloma cells, a combination of lenalidomide with panobinostat, another HDAC inhibitor, has shown additive or greater activity in both *in vitro* and *in vivo* models. [Ocio E, 2007; Ocio E, 2010] The study of the combination of a HDAC inhibitor and lenalidomide are ongoing in patients with relapsed and refractory multiple myeloma. In two phase I dose finding studies, the oral HDAC inhibitor vorinostat has been safely combined with lenalidomide at the MTD and full standard approved doses ( 400 mg of vorinostat and 25 mg lenalidomide) of each drug alone without significant dose limiting toxicities [Siegel D 2009; Kaufman J 2010; Richardson P, 2010].

Among novel, non-chemotherapeutic agents, lenalidomide and romidepsin have shown significant activity in a broad range of lymphoid malignancies with good safety profiles, absence of cumulative toxicities, and fundamentally different mechanisms of action than the chemotherapies to which most patients are initially exposed. Among the HDAC inhibitors, romidepsin has shown the most potent clinical activity when similar diseases have been studied. And based on the phase I experience with vorinostat and lenalidomide, it is likely that these two agents can be safely combined at active single agent doses without excess toxicity in heavily pretreated patients. Therein lies the fundamental rationale for this research.

## 4.0 OVERVIEW OF STUDY DESIGN/INTERVENTION

### 4.1 Design

**Phase Ib:** The phase Ib portion of the study is designed to determine the MTD of romidepsin and lenalidomide. All patients must have a relapsed or refractory B-cell lymphoma, T-cell lymphoma, or multiple myeloma. Patients will be treated on a 28-day cycle with romidepsin infused on day 1, 8, and 15, and lenalidomide taken orally on days 1-21. The design is a standard 3+3 dose escalation (Table 1) of romidepsin and lenalidomide. The first cohort will enter at dose level 1.

Dose Level	Romidepsin	Lenalidomide
-1	8 mg/m 	10 mg
1	8 mg/m 	15 mg
2	8 mg/m 	25 mg
3	10 mg/m 	25 mg
4	14 mg/m 	25 mg

Table 1: Description of dose level

DLT is defined in cycle 1 (in phase Ib).

Definitions:

- Grade  $\geq$  3 non-hematologic (attributed to study drugs)
- Grade 4 hematologic toxicities (attributed to study drugs) defined as:
  - Grade 4 thrombocytopenia (platelets  $< 25$  K/ $\mu$ L)
  - Grade 4 neutropenia (absolute neutrophil count (ANC)  $< 0.5$ )
- Grade 3 thrombocytopenia or neutropenia that results in a  $> 3$  day delay in any romidepsin dose in cycle 1.
- One week or greater delay in initiating cycle 2 day 1 due to continued drug-related toxicity.

Any patient with an adverse event that meets the DLT definition is considered evaluable for MTD determination. Patients who do not have a DLT, but received  $<3$  doses of romidepsin or  $<80\%$  (17/21) of the doses of lenalidomide during cycle 1 will not be evaluable for MTD and will be replaced.

Three patients will be initially treated in each cohort until the MTD is determined. If dose level 4 (full dose of each drug) is achieved without DLT after 1 cycle that dose level will be deemed the optimal dose and the study will proceed to a phase IIa expansion cohort. Patients treated at MTD in the phase Ib portion will be counted towards the phase IIa accrual by disease subtype and also for all efficacy and toxicity endpoints unless they did not have measurable disease at point of study entry as allowed in the phase Ib portion.

**Phase IIa:** The phase IIa portion will further assess the toxicity and safety and allow a preliminary assessment of the efficacy of the combination to provide background for a potential future subtype specific phase II study (see Section14.0).

DLT is defined in cycles 1-4 (in phase IIa)

Definitions:

- Grade  $\geq$  3 non-hematologic (attributed to study drugs)
- Grade 4 hematologic toxicities (attributed to study drugs) defined as:
  - Grade 4 thrombocytopenia (platelets  $< 25$  K/ $\mu$ L)
  - Grade 4 neutropenia (absolute neutrophil count (ANC)  $< 0.5$ )
- Grade 3 thrombocytopenia or neutropenia that results in a  $> 4$  day delay in any romidepsin dose in cycle 1.
- One week or greater delay in initiating cycle 2 day 1 due to continued drug-related toxicity.

At the time of enrollment the patients will be identified as representing three cohorts based upon disease subtype: 1) B-cell lymphoma 2) multiple myeloma 3) PTCL. Each disease specific cohort will enroll 15 patients. We plan to accrue 38 patients into the phase IIa portion including those treated at the MTD of the phase Ib portion. The assessment of toxicity and efficacy will be performed within the entire cohort evaluable at MTD. A preplanned exploratory analysis of the toxicity and efficacy of the disease specific cohorts will also be performed. Efficacy measures which will be determined include ORR, CBr (for myeloma), TTR, DOR, and EFS. ORR is defined as the percentage of patients achieving a best response of CR/CRu, very good partial response (VGPR--myeloma only), or PR at any disease assessment time point. CBr is defined as CR, VGPR, PR or MR (minimal response) in myeloma patients. TTR is defined as the time or number of cycles between study registration and documentation of first response (CR/Cru, VGPR, or PR). DOR is defined as the time or number of cycles between documentation of first response and progression, change of therapy, death, or date of last contact (if still alive without progression). EFS is defined as the time between study registration and documented progression, change in therapy, or death if no progression was observed.

[figure not shown]

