## **6.0 CRITERIA FOR SUBJECT ELIGIBILITY.**

### **6.1 Subject Inclusion Criteria**

1. Pathology confirmed lymphoma or multiple myeloma.
  - Hodgkin lymphoma is eligible for either phase and will be considered a B-cell lymphoma in the phase IIa study.
  - Phase IIa portion, subjects must have B-cell lymphoma, T-cell lymphoma, or multiple myeloma.
2. Relapse or progression after at least 1 systemic therapy.
3. Measurable disease for phase IIa portion only.

- Lymphoma (includes CTCL patients who are NED in skin): CT or PET/CT by modified Cheson criteria with incorporation of PET.
  - Multiple myeloma: Patient must have measurable disease and therefore must have at least one of the following:
    - i. Serum M-protein  $\geq 0.5\text{gm/dL}$  ( $\geq 5\text{gm/L}$ )
    - ii. Urine M-protein  $\geq 200\text{mg/24hr}$
    - iii. Serum FLC assay: involved FLC  $\geq 10\text{mg/dL}$  ( $\geq 100\text{mg/L}$ ) provided serum FLC ratio is abnormal.
  - CTCL: mSWAT  $>0$ , or absolute Sezary count  $\geq 1000\text{ cells}/\mu\text{L}$ .
4. Age  $\geq 18$  years at the time of signing the informed consent form.
  5. Able to adhere to the study visit schedule and other protocol requirements.
  6. Previous systemic anti-cancer therapy must have been discontinued at least 3 weeks prior to treatment in this study. If there is progression of disease on that therapy and all adverse effects have resolved to Grade 1 or baseline, in which case 2 weeks is acceptable.
  7. Previous radiation, hormonal therapy, and surgery must have been discontinued or completed at least 2 weeks prior to treatment in this study and adverse effects must have resolved. Lymph node or other diagnostic biopsy within 2 weeks is not considered exclusionary.
  8. Short course systemic corticosteroids for disease control, improvement of performance status or non-cancer indication (< 7 days) must have been discontinued at least 7 days prior to study treatment. Stable ongoing corticosteroid use ( $\geq 30$  days) up to an equivalent dose of 15 mg of prednisone is permissible.
  9. ECOG performance status of  $\leq 2$  at study entry (see Appendix A).
10. Laboratory test results within these ranges:
- Absolute neutrophil count  $\geq 1.0/\text{mm}^3$ .
  - Platelet count  $\geq 70\text{ K}/\mu\text{L}$ , if thrombocytopenia is due to bone marrow involvement platelet count must be  $\geq 50\text{ K}/\mu\text{L}$ .

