**\*1 cycle equals 28 days**

### **9.3 Treatment Plan romidepsin/lenalidomide Phase IIa**

The entire accrual is planned to have up to 51 patients in the phase IIa portion; each disease cohort will have 15 patients (B-cell lymphoma, multiple myeloma or PTCL). There will be an expansion of the T-cell cohort to include an additional 6 patients with acute T-cell leukemia/lymphoma. After a sufficient number of patients have been enrolled for determination of the primary and secondary objectives, cohorts may be closed to accrual by the MSK principal investigator. The MTD for lymphoma has been determined to be 14mg/m^2 romidepsin on Days 1, 8, 15 and 25mg lenalidomide from Days 1-21. The patients treated at MTD in the phase Ib cohort (if measurable disease at enrollment) and phase IIa cohort will be evaluated both collectively and by disease subtype. Patients with more than one histology are eligible and will be assigned by the principal investigator to a specific disease subtype.

- In patients with MM, due to the presence of toxicities, patients will be dosed at romidepsin 10mg/m^2 and lenalidomide 25mg (see table 2a). If two of six (or fewer) patients treated at this dose level develop dose-limiting toxicities, the initial dosing for subsequent patients will be decreased to romidepsin

10mg/m^2 and lenalidomide 15mg. For example, if two of four patients treated at this initial dose develop dose-limiting toxicities, the starting dose for subsequent patients will be reduced as above.

- At a starting dose of romidepsin 10mg/m^2 and lenalidomide 15mg, should 2 of 6 (or less) patient will be reduced to romidepsin 8mg/m^2 and lenalidomide 15mg.
- At a starting dose of romidepsin 8mg/m^2 and lenalidomide 15mg, should 2 of 6 (or less) patients have dose-limiting toxicities, the initial dose for subsequent patients will be reduced to romidepsin 8mg/m^2 and lenalidomide 10mg.

Table 2a: Multiple Myeloma Dosing for Phase IIa Portion

Dose level	Romidepsin	Lenalidomide
1	10	25
-1	10	15
-2	8	15
-3	8	10

The treatment plan for the phase IIa portion is described below:

Romidepsin/Lenalidomide Cycle 1 Day 1 + subsequent Cycle X

Romidepsin MTD IVPB over 4 hours

Lenalidomide MTD PO q days 1-21

Romidepsin/Lenalidomide Cycle 1 Day 8

Romidepsin MTD IVPB over 4 hours

Romidepsin/Lenalidomide Cycle 1 Day 15

Romidepsin MTD IVPB over 4 hours

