## **9.7 Dose Continuation, Modification and Interruption**

Subjects will be evaluated for AEs at each visit with the NCI CTCAE v4.0 (Appendix H): NCI CTCAE v4.0) used as a guide for the grading of severity. DLTs as defined will be tabulated in cycle 1 of the phase Ia and cycles 1-4 of the phase IIa portion of the study. The toxicity decision rule for the IIa portion is described in Section 14.0. The sections below describe dose reduction steps, instructions for initiation of a new cycle of therapy and dose modifications during a cycle of therapy. Inability to meet treatment criteria will result in holding the dose.

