## 14.0 BIOSTATISTICS

The standard dose-escalation scheme for this study is as follows. Patients will be accrued to the study in cohorts of 3. For any given dose an initial cohort of 3 patients will be treated at that dose. The dose level will be escalated if none of the 3 patients exhibits any DLT in the first cycle as defined in section 4.1. If a DLT is observed in one patient, an additional cohort of 3 patients will be treated at that dose. The dose will be escalated if none of the additional 3 patients exhibits any DLT. Dose-escalation stops and the previous dose will be considered the MTD if 2 or more patients have a DLT. If the previous dose level has been administered to only 3 patients, an additional 3 patients will be enrolled to confirm the result. For this design the probability of escalation is as follows:

True toxicity rate	5%	10%	15%	20%	25%	30%	40%	50%
Probability of escalation	0.97	0.91	0.81	0.71	0.60	0.49	0.31	0.17

Dose escalation will start with dose level 1. A dose level -1 is also added to the design to ensure a minimum level of toxicity (we expect this dose level will be quite tolerable for patients). The maximum number of patients needed for this dose escalation design is 30. Patients with measurable disease treated at MTD in the phase Ib will be analyzed in phase Ila to further characterize the toxicity of romidepsin and lenalidomide in combination at the MTD determined by phase Ib. In phase Ila, we plan to enroll about 39 patients so that the total number of patients to be treated at MTD will be approximately 44 (we plan to enroll 15 patients with B-cell lymphomas, 8 patients with multiple myeloma, 15 patients with T-cell lymphomas and additional 6 patients with acute T-cell leukemia/lymphoma). To subsequently monitor the safety primary endpoint in the phase Ila portion, we will employ a dose-reduction plan for the predefined DLT in the phase Ib portion during cycles 1-4. This dose-reduction plan specifies that the dose will be reduced from the phase Ib MTD to the MTD-1 (10mg/m^2 romidepsin; 25mg lenalidomide) if DLT occur in cycle 1-4 in: ≥8/first 15; ≥16/first 30; or if more than 24 patients when the last (45th) evaluable patient has completed the trial have any DLT. If at MTD-1 a DLT occurs in ≥8/first 15; ≥16/first 30, then MTD-2 (8mg/m^2 romidepsin; 25mg lenalidomide) will be employed for the remainder of phase Ila. The probability of dose-reducing from the MTD is the following:

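### The pooled toxicity analysis at the MTD leaves out phase Ib patients without measurable disease, a condition that bears on response and not on toxicity

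*Combined protocol and SAP*

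**What the plan says.** Three sections set the rule for carrying phase Ib patients forward.

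- Section 4.1 (Design) counts those treated at the MTD towards phase IIa accrual and "also for all efficacy and toxicity endpoints unless they did not have measurable disease" at study entry.
- Section 9.3: "The patients treated at MTD in the phase Ib cohort (if measurable disease at enrollment) and phase IIa cohort will be evaluated both collectively". A breakdown by subtype is planned as well.
- Section 14.0: "Patients with measurable disease treated at MTD in the phase Ib will be analyzed in phase" IIa. The stated purpose is to characterize further the toxicity of the combination at the MTD.

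Section 6.1 lists the eligibility item as "Measurable disease for phase IIa portion only", so a patient without measurable disease could enter phase Ib. Section 2.0 makes safety and toxicity part of the primary objective.

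On tabulation, section 9.7 says: "DLTs as defined will be tabulated in cycle 1 of the phase Ia and cycles 1-4 of the phase IIa portion of the study" (the first phase is Ib elsewhere in the protocol). Section 14.0 plans an analysis of serious adverse events for all patients. Section 17.2.1, under Adverse Event Reporting, requires every adverse experience to be recorded and assessed.

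On numbers, section 14.0 says: "we plan to enroll about 39 patients so that the total number of patients to be treated at MTD will be approximately 44". Its breakdown is 15 B-cell, 8 myeloma, 15 T-cell and 6 acute T-cell leukemia/lymphoma patients.

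**The concern.** The condition sits on the wrong endpoint. A patient with nothing to measure cannot be scored for response, so leaving that patient out of a response rate is sensible. The same patient received both drugs at the MTD and is as informative about toxicity as any other. No reason is given for the restriction.

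Within section 14.0 the condition is even reversed. It is attached to the toxicity sentence, but it is missing from the later sentence that pools the disease subtypes for the response and time-to-event endpoints and adds the phase Ib patients treated at the MTD.

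The MTD-level toxicity profile is a primary result, and section 4.1 intends phase IIa as background for a possible subtype-specific phase II study. It should describe everyone treated at that dose.

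**Working it through.** **1. Where an excluded patient's events go.** Take a phase Ib patient treated at the MTD without measurable disease.

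| Event | Where the plan analyses it |
|---|---|
| DLT in cycle 1 | Phase Ib DLT count and MTD decision (sections 4.1, 9.7, 14.0) |
| Serious adverse event, any cycle | All-patient analysis (section 14.0) |
| Non-serious DLT-level event, cycles 2-4 | Recorded, but in no planned DLT tabulation |

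The third row follows from section 9.7. The first phase is tabulated in cycle 1 only. The cycle 1-4 tabulation belongs to phase IIa, which this patient does not join. A phase Ib patient with measurable disease does join it.

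**2. The plan's own total.** 15 + 8 + 15 + 6 = 44, which agrees with the stated figure. 44 - 39 = 5 is the implied carry-over, but both figures are given as approximate.

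**3. Bound on the effect.** Let n be the number in the pooled set under the rule, x the number with the event, and k the number excluded. The documents do not give k; it may be 0, and I assume 1 to 3 for illustration. Adding everyone back puts the rate between x/(n+k), if no excluded patient had the event, and (x+k)/(n+k), if all did. Whatever x is, the shift from x/n is at most k/(n+k).

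Two values of n are used. One is 44. The other is 15 + 15 + 6 = 36, which drops the 8 myeloma patients because section 9.3 starts them at a different dose from the lymphoma MTD. The illustrative rate is an assumed 25%, that is 11/44 or 9/36.

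| k | n = 44: range | n = 44: largest shift | n = 36: range | n = 36: largest shift |
|---|---|---|---|---|
| 1 | 11/45 to 12/45 = 24.4% to 26.7% | 1/45 = 2.2 points | 9/37 to 10/37 = 24.3% to 27.0% | 1/37 = 2.7 points |
| 2 | 11/46 to 13/46 = 23.9% to 28.3% | 2/46 = 4.3 points | 9/38 to 11/38 = 23.7% to 28.9% | 2/38 = 5.3 points |
| 3 | 11/47 to 14/47 = 23.4% to 29.8% | 3/47 = 6.4 points | 9/39 to 12/39 = 23.1% to 30.8% | 3/39 = 7.7 points |

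**4. An uncommon toxicity.** Exact (Clopper-Pearson) 95% upper limits: 0/44 gives 8.0%, and 1/45 gives 11.8%. With 36 as the base, 0/36 gives 9.7% and 1/37 gives 14.2%. One event in one excluded patient separates a toxicity that is not listed from one that is.

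**5. DLT wordings, side by side.**

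- Section 4.1, phase Ib: grade 3 cytopenia counts if it delays a cycle 1 romidepsin dose by more than 3 days.
- Section 4.1, phase IIa: the same item with more than 4 days.
- Section 14.0: phase IIa monitoring uses the DLT predefined for phase Ib, over cycles 1-4.
- Section 17.4: a different definition, based on recovery within 14 days of last treatment, with no in-cycle grade 3 delay item.
- Table 5 and the Table 7 legend: a romidepsin dose may be up to 3 days late, and Table 5 adds that omitted doses are not made up. Section 4.1 does not say whether an omitted dose counts as a delay.

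A pooled cycle 1-4 tabulation cannot be produced unambiguously until these agree.

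**The case against.** The best defence is that little or nothing is lost. MTD selection uses these patients, all adverse experiences are recorded and graded, and serious events are analysed for everyone. Phase Ib DLTs are defined in cycle 1 only, so a cycle 2-4 event in such a patient is, strictly, an adverse event and not a protocol DLT. The number affected may be zero. All of this stands, and it limits the size of the point. It does not supply a reason for tying toxicity to measurable disease, and it does not put cycle 2-4 events of DLT severity into a planned table.

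Three stronger readings are tempting, but the documents do not support them.

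- *About one patient was excluded.* A reader might set the implied carry-over of 5 against the six patients that section 9.2 mentions at dose level 4. The 5 is a difference between two rounded figures, and other planned phase IIa totals disagree (38 in section 4.1, up to 51 in section 9.3). No count can be inferred.
- *Replaced patients are dropped as well.* Section 4.1 says "The assessment of toxicity and efficacy will be performed within the entire cohort evaluable at MTD" without defining evaluable for that pool, and its phase Ib rule says that patients who had no DLT but received too few romidepsin doses or too few "of the doses of lenalidomide during cycle 1 will not be evaluable for MTD and will be replaced". Reading the second into the first is weak. The carry-over rules speak of patients treated at the MTD, with measurable disease as the only stated exception.
- *A transient cytopenia after day 15 of cycle 1 is missed by design.* Table 7 schedules no day-22 blood count, but this contradicts nothing in the plan. Table 5 requires at least weekly counts once dosing is held. An extra draw would be a preference.

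**Conclusion.** The point holds as a problem of analysis-set definition. Sections 4.1, 9.3 and 14.0 apply a response criterion to a primary safety analysis. It does not show that the MTD was wrongly chosen or that safety data are lost, and the direction of any effect is unknown.

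The size is small: at most about 2.2 percentage points per excluded patient on a base of 44, or 2.7 on a base of 36. These figures rest on the planned totals in section 14.0 and on an assumed k of 1 to 3; if k is 0, nothing changes. The more practical risk is that an uncommon toxicity goes unlisted in the MTD-level tables.

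Mixing starting doses is a related weakness. The 8 myeloma patients are 8/44 = 18% of the set that section 14.0 describes as treated at the MTD, although section 9.3 starts them at another dose. The correction is worth making because it is simple and uses data already collected.

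**What to change.** 1. In sections 4.1, 9.3 and 14.0, apply the measurable-disease condition to efficacy endpoints only, and add it to the section 14.0 sentence that pools patients for response.
2. Define the toxicity set as every patient treated at the MTD in phase Ib or IIa. Tabulate toxicity and cycle 1-4 DLT-level events for that set, and report how many had no measurable disease.
3. Show toxicity by starting dose, so that myeloma patients started at another dose are not mixed with those at the lymphoma MTD.
4. State that the added phase Ib patients enter the descriptive toxicity tables only and do not retrospectively change the first-15 and first-30 dose-reduction counts in section 14.0.
5. Separately, reconcile the DLT wordings in section 4.1 (both phases), section 14.0 and section 17.4 with the late- and omitted-dose text in Table 5 and the Table 7 legend. Which wording should govern is for the investigators to decide.

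The cost is amendment wording and some extra tables from data already collected. Reported toxicity rates may move slightly in either direction.
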